8.8. Development Safety Update Reports

The CI will submit (in addition to the expedited reporting above) DSURs once a year throughout the clinical trial, or on request, to the Competent Authority (MHRA in the UK), Ethics Committee, Host NHS Trust and Sponsor.

9. STATISTICS

9.1. Sample size

This is a non-randomised multi-centre phase I/II study. The trial will be open label; given the objective nature of the measurements, this is unlikely to introduce significant bias in assessing key outcomes. Study ID will be assigned to participants in the order in which they are enrolled in the trial. The correspondence between the subject study ID and the treatment number/arm allocation will be noted down in the CRF and subsequently entered in the OpenClinica system.

The total number of subjects enrolled to the study will be 36: 12 subjects with low- or intermediate-risk localised or locally advanced prostate cancer and 24 subjects with metastatic disease.

In this adaptive design study, the sample size of each patient cohort is chosen to allow an initial descriptive report of the safety of the vaccine in combination with checkpoint blockade. In this study, we are targeting a 25% response rate to the vaccine in combination with PD-1 blockade in mCRPC patients. The sample size of 24 patients in Group 2 will require that 6 out of 24 treated patients will have a complete response, partial response or stable disease. The patient cohorts recruited to the KEYNOTE-199 study will serve as a control group for ADVANCE and 11% overall response rate to PD-1 blockade as a monotherapy will be compared with the response rate to the vaccine in combination with anti-PD-1 treatment in the ADVANCE patients.

The 12 patients in the surgical group will be compared for response rate to the 26 surgical subjects treated with the same vectored vaccines but no anti-PD1 in the VANCE trial. None of the 26 patients in VANCE showed a significant reduction in PSA levels during that trial. The

sample size of 12 is chosen to allow an initial descriptive comparison of response rates with and without anti-PD1 to help power any potential future trial.

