Encouragingly, the first meaningful evidence of PD-1 clinical activity in advanced metastatic prostate cancer has recently emerged. Graff and colleagues enrolled 27 men with mCRPC progressing on the androgen receptor antagonist enzalutamide (ENZ) and treated them with anti-PD-1 mAb pembrolizumab. Five of the 27 treated patients demonstrated a strong response to the treatment, with a 99% PSA reduction and observed shrinkage of measurable tumour lesions (ESMO 2017).

A large multi-centre international trial, KEYNOTE-199, to evaluate pembrolizumab as a monotherapy in 370 patients with metastatic castration resistant prostate cancer previously treated with docetaxel-based chemotherapy is currently ongoing (NCT02787005). Groundbreaking preliminary results from 258 patients already recruited to the trial were reported by De Bono and colleagues at the ASCO annual meeting in June 2018 (J Clin Oncol 36, 2018 (suppl; abstr 5007). It was demonstrated that pembrolizumab has antitumour activity in both PD-L1 positive and PD-L1 negative patients with mCRPC, as shown in the figure below. Across all cohorts, disease control rate lasting \geq 6 months was 11% in both RECIST-measurable and non-measurable disease.

Metastatic castration-resistant prostate cancer is genetically heterogeneous and includes DNA repair defective subtypes. DNA repair defects were suggested to be associated with pembrolizumab anti-tumour activity in this study. These data support further evaluation of anti PD-1 therapy in mCRPC and, in particular, in combination with vaccines that would provide a tumour-associated antigen as an alternative to naturally occurring mutated antigens.

Change From Baseline in Sum of Target Lesions, Cohorts 1+2

^aPercentages are calculated out of the [163 patients](#) who had ≥ 1 post-baseline scan evaluable per RECIST v1.1 by independent, central review. Data cutoff date: Oct 13, 2017.

Presented By Johann De Bono at 2018 ASCO Annual Meeting

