In ADVANCE, we are targeting a 25% or greater response rate to the vaccine in combination with PD-1 blockade in mCRPC patients. The sample size of 24 patients in Group 2 will require that 6 out of 24 treated patients will have complete response, partial response or stable disease. The patient cohorts recruited to the KEYNOTE-199 study will serve as a control group for ADVANCE and 11% overall response rate to PD-1 blockade as a monohterapy will be compared with the response rate to the vaccine in combination with anti-PD-1 treatment in the ADVANCE patients. If six of 24 treated patients do respond as described the would be a significantly ($P < 0.05$, two-tailed) higher rate than in the KEYNOTE-199 series and suggest added value to use of the viral vectors, supporting their assessment in a future larger scale trial.

Route of injection

The choice of the intramuscular route for ChAdOx1 vector is based on the assumption that no co-infection of natural human adenovirus could occur at this site. Furthermore, there is a large body of data from human clinical trials using replication defective Ad5- and Ad6-based HIV vaccines injected intramuscularly showing an excellent safety profile, no viral shedding, and high levels of immunogenicity. MVA.5T4 will also be given by the intramuscular route following data from [name] showing enhanced immunogenicity and less local reactivity (study VAC033) when MVA vectors are administered via the intramuscular compared to subcutaneous route.

Anti-PD-1 monoclonal antibody will be administered by intravenous infusion as per the SmPC.

[figure not shown]
Vaccine and immune checkpoint inhibitor dose

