The response to treatment in patients with measurable disease will be evaluated per Response Evaluation Criteria In Solid Tumours 1.1 (RECIST 1.1) and per immune-related response criteria (iRECIST).

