9.2. Analysis

A detailed statistical analysis plan (SAP) will be prepared and finalised with the study statistician before the first interim data analysis.

Data analysis of the following endpoints: safety, efficacy and immunogenicity will be assessed as detailed in Section 7. Safety data will be presented according to frequency, severity and duration of adverse events. Efficacy analysis will be primarily based on evaluation of ctDNA reduction, PSA response rate, radiographic progression-free and overall survival between metastatic PCa study arms. Immunogenicity will consist of descriptive analysis of cellular and humoral immune responses to the vaccine transgene in the circulation, focusing on the magnitude and qualities of T cell responses.

Exploratory analyses may also include, but are not limited to, the analyses described below:
Factors predictive of treatment benefit: baseline demographic, tumour status, haematological or immunological variables may be included as interactions with treatment in logistic, longitudinal or proportional hazards models of efficacy endpoints in order to assess their value as factors predictive of treatment benefit.

Factors predictive of immune response: baseline demographic, tumour status, haematological or immunological variables may be included as explanatory variables in models of qualitative and quantitative immunological endpoints in order to assess their value as factors predictive of immune response.

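### Group 2's only numerical efficacy target (6/24 with complete response, partial response or stable disease, against 11%) is not set on the primary endpoint, and the 11% is mislabelled as an overall response rate

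*Protocol*

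**What the plan says.** - **Target (Protocol 9.1, also 2.2).** The target for Group 2 is 25%, expressed as "6 out of 24 treated patients will have a complete response, partial response or stable disease". Section 9.1 first says that "the sample size of each patient cohort is chosen to allow an initial descriptive report of the safety", and it claims no power.
- **Comparator (9.1, also 2.2).** The "11% overall response rate to PD-1 blockade as a monotherapy will be compared with the response rate to the vaccine" plus anti-PD-1 in ADVANCE, with the KEYNOTE-199 cohorts serving as control group.
- **Origin of the 11% (2.2).** It is introduced as a disease control rate lasting at least "6 months was 11% in both RECIST-measurable and non-measurable disease", from a trial in men previously treated with docetaxel.
- **Inference (2.2).** "If six of 24 treated patients do respond as described the would be a significantly" higher rate (P < 0.05, two-tailed), which would "suggest added value to use of the viral vectors, supporting their assessment in a future larger scale trial".
- **Primary efficacy endpoint (3, 7.1).** This is a composite: a fall of at least 50% in PSA or in ctDNA, at 24 weeks or at any time.
- **Analysis (9.2).** "Efficacy analysis will be primarily based on evaluation of ctDNA reduction, PSA response rate, radiographic progression-free and overall survival". Complete response, partial response or stable disease (CR/PR/SD) is not listed here or as an endpoint in Section 7.
- **Radiological response (6.2).** "The response to treatment in patients with measurable disease will be evaluated per Response Evaluation Criteria In Solid Tumours 1.1" and iRECIST, with scans at baseline, 6 and 12 months.

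**The concern.** The target is set on one outcome and the primary efficacy analysis on another. Section 9.1 speaks of comparing the response rate in ADVANCE with 11%, but the only response rate that Section 7 defines for Group 2 is the PSA/ctDNA composite. A reader could therefore test the composite against a figure that measures something else, or choose between the two outcomes once the data are seen.

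The outcome behind 6/24 is itself incomplete. No duration is attached to stable disease, while the 11% requires at least 6 months of control. The only rule for judging response covers measurable disease, while the denominator is all 24 men. Section 5.3 does not require measurable disease and admits men on PSA progression or progressive bone metastases alone.

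At stake is the signal that Section 2.2 links to a larger trial. It rests on an outcome that Section 7 does not define, a mislabelled comparator, and a significance claim made for the result exactly at the threshold.

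**Working it through.** **1. Endpoint against target**

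| Item | Outcome | Benchmark | Where |
|---|---|---|---|
| Primary efficacy endpoint | Fall of at least 50% in PSA or ctDNA | None | 3, 7.1 |
| Numerical target | CR, PR or SD in 6/24 | 11% | 2.2, 9.1 |
| The 11% as introduced | Disease control lasting at least 6 months, measurable and non-measurable disease | n/a | 2.2 |
| The 11% as used | Overall response rate | n/a | 2.2, 9.1 |

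An overall response rate ordinarily excludes stable disease. The 6/24 criterion and the 11% both count it, so the label fits neither.

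**2. The plan's own figure**

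Inputs: n = 24 and target 25% (9.1); reference 11% and two-tailed P < 0.05 (2.2).

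- 0.25 × 24 = 6.
- Exact binomial upper tail, P(X ≥ 6 | n = 24, p = 0.11) = 0.0417.
- The exact two-sided test that adds all outcomes no more probable than the observed one also gives 0.0417. P(X = 0) = 0.061 exceeds P(X = 6) = 0.029, so nothing is added from the lower tail.
- Normal score test without continuity correction: z = (0.25 − 0.11)/√(0.11 × 0.89/24) = 2.19, p = 0.028.

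So the P < 0.05 statement reproduces under some tests with 11% treated as known.

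**3. Other standard choices, 11% still treated as known**

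- Doubled exact tail: 2 × 0.0417 = 0.083.
- Score test with continuity correction: p = 0.062.
- Exact (Clopper-Pearson) 95% CI for 6/24: 9.8% to 46.7%, which includes 11%. The Wilson interval, 12.0% to 44.9%, excludes it.

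**4. Allowing for sampling error in the reference**

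Assumption: the 11% applies to all 258 men. The protocol gives no count; 28/258 = 10.85% and 29/258 = 11.24% both round to 11%.

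| Comparison | Fisher, two-sided | Chi-square, uncorrected | Chi-square, corrected |
|---|---|---|---|
| 6/24 vs 28/258 | 0.053 | 0.042 | 0.088 |
| 6/24 vs 29/258 | 0.096 | 0.051 | 0.103 |
| 7/24 vs 28/258 | 0.018 | 0.009 | 0.023 |
| 7/24 vs 29/258 | 0.021 | 0.012 | 0.028 |

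Against a fixed 11%, 7/24 gives 0.0124, or 0.0248 doubled. Among these tests, then, the fragility is confined to the stated threshold of six.

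**5. Sensitivity to the reference rate**

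P(X ≥ 6 of 24) exceeds 0.05 once the true reference rate passes 11.5%, exceeds 0.10 once it passes 13.7%, and is 0.139 at 15%. The exact 95% CI for 28/258 is 7.3% to 15.3%, so such rates are compatible with the reference data.

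**6. What 6/24 would mean on the composite**

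The protocol gives no reference rate for the composite. As an illustration only, Section 2.2 reports a strong PSA response in 5 of 27 men (18.5%) given pembrolizumab after progression on enzalutamide. At that rate P(X ≥ 6 of 24) = 0.277, so six composite responders would be unremarkable.

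**7. Denominator and timing (both rest on assumptions)**

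- The number with measurable disease is not given. If it were 12 to 18 of 24, six men with RECIST CR, PR or SD would be 6/12 = 50% to 6/18 = 33% of those assessable, not 25%.
- If visit V11 is week 24, its scan falls 168 days (5.5 months) after enrolment and 140 days (4.6 months) after the first nivolumab dose at week 4. One such scan only approximates control lasting at least 6 months.

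**The case against.** The strongest reply is that nothing operational turns on 6/24. Section 9.1 sizes the cohorts for a descriptive safety report. Section 4.1 bases interim review and any sample-size re-calculation on ctDNA, PSA kinetics and immune responses. The monitoring rules in 5.7 and 8.7 do not mention 6/24, and Section 2.2 says only that the result would suggest added value. This stands as far as it goes: 6/24 is not a stopping or adaptation rule. But it is the only stated efficacy target and the stated support for a larger trial, and Section 4.1 widens the gap by steering the adaptation with the other outcome.

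Second, CR, PR or SD is a disease-control type of measure, and stable disease at the first on-study scan at 6 months would approximate 6-month control. That is true, and it makes the 11% closer in kind to the target than its label suggests. It does not make disease control an endpoint, set a duration or cover non-measurable disease.

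Third, the P < 0.05 claim is not an arithmetic error: it reproduces under the exact two-sided test and the uncorrected score test. This is accepted. The fault is an unqualified claim that several equally standard tests do not support.

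Fourth, the duration of stable disease and the handling of non-measurable disease could be left to an SAP. Those details could. But the target, comparator, label and significance claim are fixed in the protocol, and an SAP that follows Section 7 would contain no outcome to which 6/24 applies.

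**Conclusion.** The concern holds and needs correcting. Two faults follow from the text alone, without any assumption: the only numerical efficacy target for Group 2 is not on the primary efficacy endpoint, which has no benchmark, and the 11% is a disease control rate of at least 6 months carried forward as an overall response rate.

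The significance claim is a further, smaller weakness. At exactly 6/24 the two-sided p runs from 0.028 to 0.083 against a fixed 11%, and from 0.042 to 0.103 if the reference is 28 or 29 of 258 men, which is an assumed count. At 7/24 every comparison in the table of step 4, and the exact test against a fixed 11% even when doubled, is below 0.05.

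The populations may also differ: the reference trial is described as post-docetaxel, while Section 5.3 allows prior chemotherapy but does not require it. A result of 6/24 would not by itself show that the vaccine added to anti-PD-1. The denominator and scan-timing figures are illustrative, and the conclusion does not depend on them.

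**What to change.** 1. In Sections 2.2 and 9.1, relabel the 11% as a disease control rate lasting at least 6 months.
2. Reconcile Sections 2.2, 6.2, 7 and 9.1 by stating which endpoint 6/24 judges.
   - If disease control: add it to Section 7.2 as a secondary endpoint, define it for measurable and non-measurable disease from the scheduled scans, and say that one scan at about 6 months only approximates control lasting at least 6 months.
   - If the primary composite: drop the 11%, and state and justify a benchmark for that endpoint.
3. In either case, report the composite with an exact 95% CI (for example 6/24: 9.8% to 46.7%) and do not test it against 11%.
4. Describe the historical cohort as an unmatched external reference. In Section 2.2, replace the claim of a significantly higher rate with a statement that 6/24 would be a supportive signal for a larger trial, not evidence by itself of added vaccine value.

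**Cost.** The change needs protocol wording plus a short definition of disease control in non-measurable disease, or a justified benchmark if the composite is chosen. Adding an endpoint may need a substantial amendment with the usual approvals. No visits, scans or samples are added, because the scans, PSA and ctDNA are already scheduled. The price is a weaker efficacy claim.

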A new class of anti-cancer drugs termed immune checkpoint inhibitors (CPIs) has recently emerged. These belong to a category of antigen non-specific immunotherapies, in contrast to Provenge and PROSTVAC. The immune system is capable of recognising and eliminating cancer but it is held in check by inhibitory receptors and ligands. These immune checkpoint pathways, which normally maintain self-tolerance and down-regulate immune responses to pathogens to limit collateral tissue damage, can be co-opted by cancer to evade immune destruction. The novel drugs are the molecules that interrupt these immune checkpoint pathways and thus unleash anti-tumour immunity. The monoclonal antibodies (mAbs) against CTLA-4 (Cytotoxic T-lymphocyte-associated antigen 4), PD-1 (Programmed Death-1) and PD-L1 (Programmed Death Ligand-1) are the first drugs having entered the clinic as immunotherapies, and they have been licenced for advanced melanoma, lung, bladder, kidney cancers and other cancer types^{6,7}.

It is noteworthy that cancer types with the highest response rate to PD-1 blockade are the ones with the highest mutational load. Mutated proteins can give rise to neoantigens that are likely to be recognized by the host immune system and generate a spontaneous anti-tumour immune

response. Prostate cancer is known to have a relatively low mutational burden and this may, at least in part, explain the observation that checkpoint inhibitors have shown limited clinical benefit in prostate cancer to date^{8,9}. However, the data from the ongoing KEYNOTE-199 study (NCT02787005) reported (by de Bono et al.) at the ASCO annual meeting in June 2018 (abstract number 5007) demonstrate that anti PD-1 therapy had clinical activity in 11% of 258 metastatic castration-resistant prostate cancer patients. These drugs are even more likely to be clinically effective in prostate cancer if they are delivered in combination with an immunogenic vaccine, thus circumventing the need for tumour-specific neoepitopes in order to induce spontaneous anti-tumour immune responses.

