A second trial cohort in this study will comprise patients with metastatic castration resistant prostate cancer (mCRPC) with evidence of progression on anti-androgens. In the CRPC setting, the primary successful therapeutic target remains the androgen receptor. Intensive research into androgen receptor resistance mechanisms has enabled effective new treatments - androgen synthesis pathway targeting agents, such as abiraterone, and direct inhibitors of the androgen receptor, such as enzalutamide (ENZ). All patients with CRPC will ultimately succumb to the disease in the absence of a competing cause of mortality. The majority of prostate cancer vaccine monotherapies have to date been tested in this patient cohort and have demonstrated significant but only modest survival benefit.

Whilst CRCP patients have shown resistance to immune checkpoint blockade²⁹⁻³¹ until recently, there are several lines of evidence to indicate that metastatic patients who are resistant to the second generation anti-androgens (particularly enzalutamide), can be particularly susceptible to immunotherapies. In one case study, a durable complete PSA response was reported in a patient progressing on ENZ following treatment with Provenge³². More recently, in a small trial of ten mCRPC patients progressing on ENZ and treated with anti-PD-1 mAb, three patients experienced rapid PSA reduction to ≤ 0.2 ng/ml³³. Although the mechanisms behind efficacy of the vaccine and checkpoint blockade in ENZ-resistant patients remain to be elucidated, there are considerable data showing that androgen-ablation may augment an anti-tumor immune response.

Second generation anti-androgen therapy represents a more potent form of androgen suppression and may therefore be associated with previously under-appreciated immune modulatory effects. Interestingly, patients progressing on ENZ had significantly increased PD-L1/2 positive dendritic cells in blood compared to treatment-naïve or those responding to treatment²⁶. These data would be consistent with the notion that responses to immunotherapy might be more common in men progressing on enzalutamide and potentially abiraterone and thus provide a rationale for selecting this patient cohort for this trial.

Early evidence of vaccine efficacy in combination with PD-1 blockade compared to PD-1 inhibition on its own will be assessed by novel genomic analysis methods, in addition to

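### The 11% benchmark for Group 2 is not secured as the no-vaccine rate for these men, and the 6-of-24 rule has almost no margin if the true rate is higher

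*Protocol*

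**What the plan says.** Section 9.1 names the comparator, "The patient cohorts recruited to the KEYNOTE-199 study will serve as a control group for ADVANCE", and the comparison: "11% overall response rate to PD-1 blockade as a monotherapy will be compared with the response rate to the vaccine in combination with anti-PD-1". It sets a 25% target and asks for 6 of 24 men with complete response, partial response or stable disease. Section 2.2 repeats this and adds the inference: 6 of 24 would be significantly higher (P < 0.05, two-tailed), would suggest that the vectors add value, and would support a larger trial.

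The external trial is described in section 2.2 as enrolling "370 patients with metastatic castration resistant prostate cancer previously treated with docetaxel-based chemotherapy is currently ongoing". The same section says of disease control lasting at least 6 months that the rate "months was 11% in both RECIST-measurable and non-measurable disease", and section 2.1 says that "anti PD-1 therapy had clinical activity in 11% of 258 metastatic castration-resistant prostate cancer patients".

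Group 2 (sections 4.3 and 5.3) is men progressing on abiraterone or enzalutamide. Earlier chemotherapy is allowed but not required, and the anti-androgen is stopped at enrolment. Section 2.2 justifies choosing this cohort on the ground that "responses to immunotherapy might be more common in men progressing on enzalutamide and potentially abiraterone".

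Two other anti-PD-1 results without vaccine matter here. For men progressing on enzalutamide, section 2.2 reports: "Five of the 27 treated patients demonstrated a strong response to the treatment, with a 99% PSA reduction". Section 2.6 reports no objective responses among 25 prostate cancer patients given single-agent nivolumab. Section 9.1 mentions neither.

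**The concern.** A single-arm result can be credited to the vaccine only if the rate that anti-PD-1 alone would give in the same men is known. The protocol takes that rate from men described by prior docetaxel, yet it selects Group 2 by progression on second-generation anti-androgens because such men may respond more often to immunotherapy. Neither section 2.2 nor section 9.1 discusses the difference.

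If the selection hypothesis is right, anti-PD-1 alone would do better than 11% in Group 2. Part or all of an observed 25% would then be credited to the vectors, and a larger trial could be started on that reading.

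**Working it through.** **Inputs.** n = 24, success count 6, null rate 11%, target 25% (sections 2.2 and 9.1). External series of 258 men (section 2.1); 0.11 × 258 = 28.4, so about 28 responders, a derived count that the protocol does not state. Other anti-PD-1 results: 5/27 = 18.5% (section 2.2) and 0/25 (section 2.6).

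**Step 1: reproduce the stated figure.** With 11% taken as fixed and X ~ Binomial(24, 0.11), P(X ≥ 6) = 1 − P(X ≤ 5) = 1 − 0.9583 = 0.0417. The two-sided exact P value that sums all outcomes no more likely than 6 is also 0.0417, because the most extreme low outcome, P(X = 0) = 0.89^24 = 0.061, is more likely than P(X = 6) = 0.029. The stated P < 0.05 therefore reproduces on this reading.

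**Step 2: vary the no-vaccine rate.** P(X ≥ 6 of 24) if the vaccine adds nothing:

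| Anti-PD-1-alone rate | P(6 or more of 24) |
|---|---|
| 11% | 0.042 |
| 11.5% | 0.050 |
| 15% | 0.139 |
| 18.5% (5/27) | 0.277 |
| 20% | 0.344 |

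The tail crosses 0.05 at about 11.5%, half a percentage point above the assumed rate. At 18.5% it is 0.277 / 0.0417 = 6.6 times its value at 11%. The expected count at 18.5% is 24 × 0.185 = 4.4, so 6 would not be the expected result, but it would not be unusual.

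**Step 3: how firm are the cited rates?**
- 5/27: exact 95% CI 6.3% to 38.1%. Over that interval P(X ≥ 6) runs from 0.003 to 0.94.
- 5/27 against about 28/258: Fisher two-sided P = 0.22.
- 0/25: exact 95% upper limit 1 − 0.025^(1/25) = 13.7%.
- 6/24, if observed: exact 95% CI 9.8% to 46.7%, which contains both 11% and 18.5%.
- 6/24 against 5/27: difference 25.0 − 18.5 = 6.5 points, Fisher two-sided P = 0.74.

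**Step 4: are the quantities alike?** The 11% is disease control of at least 6 months. The 6-of-24 rule counts complete response, partial response or stable disease, with no minimum duration given. The 5/27 are described by a 99% PSA fall and lesion shrinkage. The 0/25 are objective responses. Putting 18.5% into the rule is therefore an illustration and not the rule's false-positive rate. Counting stable disease as well could only raise the 5/27, but the protocol gives no figure for it.

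**The case against.** A reader might infer that the control cohorts were unenriched and that the benchmark is therefore biased in favour of the vaccine. The documents do not support this as fact. They say the external trial's men had received docetaxel, but not whether they had also progressed on abiraterone or enzalutamide. The two histories are compatible, and Group 2 itself admits men who have had chemotherapy. The higher responsiveness of Group 2 is worded as a possibility. The 5/27 does not differ significantly from the external series, and the 0/25 on nivolumab, the drug used here, points the other way.

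A reader might also take 5/27 as the population-matched control that should replace 11%. That fails too. The five are described by a 99% PSA fall, whereas the PSA response in section 7.1 needs only a 50% fall. The number of the 27 who reached 50% is not given, so setting a lenient count beside a strict one could itself favour the vaccine. Group 2 also takes men progressing on abiraterone. Section 2.6 describes anti-PD-1 added to continuing enzalutamide in the first ten men of a trial of this kind, whereas here the anti-androgen is stopped.

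Finally, section 9.1 calls the purpose of the sample size an initial descriptive report of safety, and section 2.2 says only that the result would suggest added value. That softens the claim. However, section 2.2 still attaches a significance statement to 6/24 and names what it would support. Comparator, rate and inference are all fixed in the protocol, so this is not a matter left to a later analysis plan.

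The objections to direction and to replacement therefore stand. The objection that 11% is adequate as the sole basis for the stated inference does not.

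**Conclusion.** The point holds as one about an unsecured null rate. The protocol's own sources do not establish 11% as what anti-PD-1 alone would give in men progressing on abiraterone or enzalutamide, and the stated inference from 6/24 fails its own 0.05 level once that rate passes about 11.5%. The chance of 6 or more of 24 without any vaccine effect is 0.14 at 15% and 0.28 at 18.5%, the latter illustrative because of the endpoint difference.

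A bias in favour of the vaccine follows only if the protocol's enrichment hypothesis is true. The calculations assume independent responses, all 24 men evaluable and a fixed comparison rate. The weakness should be corrected in the text; it does not call the design or the sample size into question.

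**What to change.** In sections 2.2 and 9.1:

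- State that the external cohorts, described by prior docetaxel, differ from Group 2, and keep 11% as one reference.
- Report the Group 2 rate with an exact 95% CI (for 6/24, 9.8% to 46.7%) beside 11% and the other cited anti-PD-1 results, including 5/27 and 0/25. Give each its caveats: endpoint, and for the enzalutamide series also the continued enzalutamide described in section 2.6 and the absence of abiraterone progressors. Call none of them population-matched.
- Replace the statement that 6/24 is significantly higher and suggests added value of the vectors. Say that 6/24 alone cannot separate a vaccine effect from a higher anti-PD-1-alone rate in this population, and show the range 0.042 to 0.28 for no-vaccine rates from 11% to 18.5%.

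The sample size, treatment and data collection do not change. The cost is rewording two sections and a few descriptive comparisons; the downside is a less favourable stated conclusion.
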